- Evaluate the complexity of cardiac surgery residents' learning curve for grafts quality assessment with HFUS as isolated technique.
- Evaluate the complexity of cardiac surgery residents' learning curve for grafts quality assessment with TTFM as isolated technique.

STUDY DESIGN AND DURATION

This is a prospective, observational, monocentric cohort study in which adult patients undergoing coronary artery bypass surgery will be enrolled.

The study will last four months: three months for patients enrollment and data collection and one month for statistical analysis and scientific paper writing.

The trial will start after obtaining favourable opinion from the local Ethics Committee and could be considered completed when all the eight cardiac surgery residents involved have reached primary endpoint.

INCLUSION CRITERIA

- Age ≥ 18 years old;
- Written informed consent;
- Indication to CABG surgery (both «on-pump» and «off-pump»);
- Stable angina, unstable angina or acute coronary syndrome without ST elevation (NSTEMI).

EXCLUSION CRITERIA

- Age ≥ 18 years old;
- Written informed consent;
- Indication to CABG surgery (both «on-pump» and «off-pump»);
- Stable angina, unstable angina or acute coronary syndrome without ST elevation (NSTEMI).

STUDY PROCEDURES

All patients with coronary artery disease and an indication for surgical revascularization (coronary artery bypass grafting) who meet the above-described inclusion and exclusion criteria will be enrolled by signing the informed consent the day before surgery.

Patient data (anamnestic data, surgery description, *intraoperative echographic and flowmetric measurements*) will be recorded in a dedicated database. All data recorded in the database are commonly acquired for all patients undergoing this type of surgery and no further examinations will be performed for patients included in the trial.

The study will involve cardiac surgery residents with different levels of training and an expert cardiac surgeon who acts as supervisor and benchmark. Each resident will sign a dedicated informed consent form in the presence of a doctor foreign to the study protocol (Cardiac Surgery ward cardiologist). The residents will be “blinded” about the trial objective and the adopted score system. They will undergo a specific training including a quick lesson and a practical workshop to familiarize with the equipment.

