The resident will acquire the TTFM recording after each graft is completed. To make the comparison as accurate as possible, the resident will perform TTFM evaluation on one graft at a time and successively the supervisor will do the same for each graft (making sure that delta between the pressure during the two recordings is lower than 10 percent and that no drug has been administered). The following items will be evaluated:

F) Time necessary to acquire the measures [$< 30 \text{ sec} \rightarrow 1$] [$> 30 \text{ sec}, < 60 \rightarrow 0.5$] [$> 60 \text{ sec} \rightarrow 0$]

G) Need for multiple measurements before the final one: [$> 2 \rightarrow 0$] [$1 \rightarrow 0.5$] [$0 \rightarrow 1$]

H) Need to change probe dimensions: [NO $\rightarrow 0$] [YES $\rightarrow 1$]

I) ACI [delta between resident and supervisor measurements $< 10\% \rightarrow 1$] [$> 10\%, < 20\% \rightarrow 0.5$] [$> 20\% \rightarrow 0$]

L) Mean Flow [delta between resident and supervisor measurements $< 10\% \rightarrow 1$] [$> 10\%, < 20\% \rightarrow 0.5$] [$> 20\% \rightarrow 0$]

M) Pulsatility Index [delta between resident and supervisor measurements $< 10\% \rightarrow 1$] [$> 10\%, < 20\% \rightarrow 0.5$] [$> 20\% \rightarrow 0$]

N) Backward Flow [delta between resident and supervisor measurements $< 10\% \rightarrow 1$] [$> 10\%, < 20\% \rightarrow 0.5$] [$> 20\% \rightarrow 0$]

O) Diastolic Filling [delta between resident and supervisor measurements $< 10\% \rightarrow 1$] [$> 10\%, < 20\% \rightarrow 0.5$] [$> 20\% \rightarrow 0$]

P) Correct interpretation of the graft quality as working [YES \rightarrow no penalty] [NO \rightarrow total score becomes 0]

Each resident will be given a TTFM-related score from a minimum of 0 to a maximum of 8.

The final score for each graft will be the sum of the two scores (HFUS and TTFM), from a minimum of 0 to a maximum of 12.

The same procedure will be repeated for each graft performed during the surgery.

Each resident will continue until reaching a ratio between total score and number of evaluated anastomoses of 11.

END-POINTS

Primary end-point

Number of anastomoses needed to reach a ratio (total score/n. of anastomoses) ≥ 11

Secondary end-points

- Number of anastomoses needed to reach a ratio (HFUS score/n. of anastomoses) = 4
- Number of anastomoses needed to reach a ratio (TTFM score/n. of anastomoses) ≥ 7

STATISTICAL ANALYSIS AND SAMPLE SIZE CALCULATION

Sample size calculation

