Our cardiac surgery unit performs between 5 and 10 coronary artery bypass grafts surgeries per week on average. Considering the inclusion and exclusion criteria and assuming that some patient may not give their informed consent, we expect to enroll 4 patients per week. Considering that the involved residents (8 in total) will take part to the procedures in turn and that we estimate around 10 surgeries to become autonomous, we estimate to enroll 80 patients during a period of 3 months.

Statistical analysis

Data will be collected in a specific database (Microsoft Excel worksheet). The Kolgomorov-Smirnov test was used to check for variables distribution. Continuous variables with a normal distribution are summarized by mean and standard deviation. Continuous variables with a non-normal distribution are expressed with median and interquartile range.

Categorical variables are reported as absolute frequency distribution and percentage. Continuous data are analyzed using the unpaired t-test or the Mann – Whitney test according to their distribution. Categorical data are compared with the Fisher's exact test. Statistical findings were considered significant if p value was less than 0.05. Statistical analysis will be performed with the statistic software SPSS (IBM).

BIBLIOGRAPHY

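### TTFM item H awards its point for a probe change, so a flawless graft without one scores only 7 (TTFM) and 11 (total), exactly the end-point thresholds

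*Combined protocol and SAP*

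**What the plan says.** In Study procedures, the TTFM assessment has eight point-scoring items (F, G, H, I, L, M, N, O). Item P adds no points but sets the score to zero if the graft is misinterpreted. Item H reads "H) Need to change probe dimensions: [NO $\rightarrow 0$] [YES $\rightarrow 1". Just above it, item G reads "Need for multiple measurements before the final one: [$> 2 \rightarrow 0$] [$1 \rightarrow 0.5$] [$0 \rightarrow 1". Item F gives its point for the fastest acquisition. Items I, L, M, N and O give theirs for the closest agreement with the supervisor.

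The range is stated as follows: "Each resident will be given a TTFM-related score from a minimum of 0 to a maximum of 8". With the HFUS score of 0 to 4, the total per graft runs from 0 to 12.

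The score drives three things:

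- the stopping rule: "Each resident will continue until reaching a ratio between total score and number of evaluated anastomoses of 11"
- the primary end-point: "Number of anastomoses needed to reach a ratio (total score/n. of anastomoses) ≥ 11"
- the TTFM secondary end-point: "Number of anastomoses needed to reach a ratio (TTFM score/n. of anastomoses) ≥ 7"

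For the expected length of training, the sample size section says "we estimate around 10 surgeries to become autonomous".

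**The concern.** Item H runs against the other seven point-scoring TTFM items, and the text gives no reason. It takes a point from a resident whose first probe fits and gives one to a resident who has to change it.

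That lost point is the whole margin between a perfect score and the threshold. The total threshold of 11 is one point below the maximum of 12, and the TTFM threshold of 7 is one point below 8. The number of anastomoses needed to reach the end-point, and the moment at which a resident stops, would then depend heavily on how often probes happen to be changed. That is not the skill the study sets out to measure.

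**Working it through.** **Inputs.** The item keys, score ranges and thresholds come from Study procedures and End-points. Two quantities are not in the documents and are assumed: the probe-change rate q (10, 20 and 30%, with higher values noted), and 2 to 4 grafts per operation. At about 10 operations per resident, the latter gives 20 to 40 anastomoses.

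**The plan's maxima.** F 1 + G 1 + H 1 + five agreement items 5 = 8. Adding HFUS 4 gives 12. Both stated maxima reproduce, but only with H = YES, that is, on a graft where the probe was changed.

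**Single grafts, printed key.**

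| Graft | TTFM | Total |
|---|---|---|
| No change, all else perfect | 1 + 1 + 0 + 5 = 7 | 11 |
| Change, all else perfect | 1 + 1 + 1 + 5 = 8 | 12 |
| Change and one repeat (G = 0.5) | 1 + 0.5 + 1 + 5 = 7.5 | 11.5 |

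**Tolerated loss.** The mean total of otherwise flawless grafts is 11 + q under the printed key and 12 − q with the key reversed. The average loss allowed on the other 11 scored items at a ratio of 11 is therefore q or 1 − q. At q = 10, 20 and 30% this is 0.1, 0.2 and 0.3 points (printed) against 0.9, 0.8 and 0.7 (reversed).

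**Recovery from one zero-scored graft.** If n later grafts average m, the ratio is n·m/(n + 1). It reaches 11 when n = 11/(m − 11), rounded up. For TTFM the counts are 7/q and 7/(1 − q), taking the zero graft to count in the TTFM denominator. If each change also costs a repeat under item G, m is 11 + 0.5q (printed) or 12 − 1.5q (reversed).

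| q | Total, printed | Total, reversed | TTFM, printed | TTFM, reversed | Total with repeat, printed | Total with repeat, reversed |
|---|---|---|---|---|---|---|
| 10% | 11/0.1 = 110 | 11/0.9 → 13 | 70 | 8 | 11/0.05 = 220 | 11/0.85 → 13 |
| 20% | 11/0.2 = 55 | 11/0.8 → 14 | 35 | 9 | 11/0.1 = 110 | 11/0.7 → 16 |
| 30% | 11/0.3 → 37 | 11/0.7 → 16 | 24 | 10 | 11/0.15 → 74 | 11/0.55 = 20 |

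**Chance of reaching 11 within N anastomoses, first graft zero and all later ones flawless.** Each 12-point graft recovers one point, so 11 are needed among N − 1. The chance is P(Bin(N − 1, q) ≥ 11) printed and P(Bin(N − 1, 1 − q) ≥ 11) reversed.

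| N | Printed, q = 10 / 20 / 30% | Reversed, q = 10 / 20 / 30% |
|---|---|---|
| 20 | <0.01 / 0.03 / 1.1% | >99.9 / 99.3 / 92% |
| 30 | 0.006 / 2 / 23% | all >99.9% |
| 40 | 0.1 / 14 / 66% | all >99.9% |

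**Milder start, printed key, N = 30.** A first graft of 10 needs one probe-change graft: 1 − (1 − q)^29 = 95%, 99.9% and >99.9%. A first graft of 9 needs two: 80%, 99% and >99.9%.

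**Higher q.** The two keys coincide at q = 50%. Beyond that they swap: at q = 70% and N = 30, after a zero first graft, the printed key gives >99.9% and the reversed key 23%.

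**Limit at q = 0.** No graft can exceed 11, so the cumulative ratio is at 11 on the first graft or never.

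**The case against.** The strongest defence is that the key may be intended. The documents do not say who picks the first probe, so YES = 1 could credit recognising a misfit. It could also be an allowance: a change takes time and may force a repeat, and if F and G each drop to 0.5 the graft scores 0.5 + 0.5 + 1 + 5 = 7, level with a flawless no-change graft. The thresholds 4, 7 and 11 = 4 + 7 would also fit an author who regarded 7 as the normal TTFM ceiling.

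Neither reading rescues the key. If it credits recognition, a resident whose first probe fits still loses a point without any error. If it is an allowance that cancels out in this way, no graft exceeds 11, the stated maxima of 8 and 12 are never reached, and the end-point becomes the first graft or never at every q. What stands is that an accidental reversal is inferred, not shown.

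The objections on size have force. A zero-scored first graft is the severe case, and a small early loss usually recovers within 30 anastomoses. The severe case is nevertheless foreseeable in learners: a wrong item E answer sets the score to zero and bars TTFM. The plan does not say whether such a graft counts in the TTFM ratio, so the TTFM recovery figures rest on the assumption that it does. The range of q is also assumed, and above 50% the comparison reverses. Finally, the cumulative ratio is a weakness in its own right, which item H aggravates but does not create.

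**Conclusion.** The concern holds. As printed, item H withholds a point from every graft that needs no probe change and places the best such graft exactly on both thresholds. This follows from the score sheet alone and needs no assumption. That the key was reversed by mistake is a strong inference, but the key fails under the other readings too.

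The practical size depends on the unknown probe-change rate and on how badly early grafts score. At 10 to 30%, one zero-scored graft puts the primary end-point largely out of reach within 20 to 30 anastomoses, while a single mild early loss is usually recoverable by 30. At any rate other than 50%, the coding of this one item changes how hard the end-point is to reach. Because it feeds the primary end-point, the TTFM end-point and the stopping rule, it must be corrected before the results can be interpreted.

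**What to change.** State in Study procedures what item H measures, then key it to match:

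- If a probe change counts as a flaw, as extra measurements do in item G, print NO → 1 and YES → 0.
- If the item is meant to credit recognising a misfit probe, give the full point also when the first probe fits. A flawless graft then scores 12 whatever the probe-change rate, and one zero-scored first graft is offset by 11 flawless ones.

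Either way 8 and 12 become attainable on a flawless graft without a probe change. Confirm the thresholds of 7 and 11 against the corrected key.

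The same edit can close a minor gap: item G has no score for exactly 2 extra measurements, and items F and I to O leave their exact cut-points unassigned. The patient data that "will be recorded in a dedicated database" do not expressly include the resident's item-level answers. Adding them would let every score and stopping point be recomputed.

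Before scoring starts, the cost is a score-sheet edit and some spreadsheet columns. If scoring has begun, re-score wherever item data exist and re-check residents who have stopped. Some may fall below 11 with no later grafts observed, and that loss cannot be repaired.

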- Backward flow (BF - percentage): it represents the percentage of flow directed from the native coronary artery to the graft during a cardiac cycle. It may indicate the presence of competitive flow between the graft and the coronary target; studies that evaluated the association between BF percentage and angiographic patency of remote graft concluded that this parameter can be considered a predictor of patency of anastomosis with an identified cut-off of 3 percent of the total flow; (5) practically, a retrograde flow area >3 percent of the total graft flow area represents a risk factor for failure.

- Diastolic filling (DF - percentage): this is a parameter that describes the mode of flow distribution according to the phase of the cardiac cycle (systole/diastole); it provides an estimate of the diastolic flow within the graft, considering that:

1) the prevalence of diastolic flow is a distinctive feature of the left coronary circulation in which coronary resistances are higher during systole for higher transmural pressure;

2) the right coronary artery supplies the right ventricular myocardium in both systole and diastole; for this reason, in this territory a DF percentage is accepted around 50 percent and it may change in case of right coronary hyper-dominance.

The correct interpretation of the TTFM requires an integration of all these parameters and their analysis also in light of the result of the intraoperative HFUS, an intraoperative imaging technique introduced in 2009. Throughout a sterile probe, this technique consents to acquire bidimensional images of the anastomoses and, in addition to TTFM, serves as a benchmark of their patency and correct shape.

Once the data obtained throughout TTFM and HFUS are combined, the surgeon can consider the graft as functioning and patent in the long term. Indeed, recent studies found out that the positive predictive value of TTFM rose from 10 percent to 100 percent when HFUS was added to the intraoperative assessment (6, 7).

Our operative unit adopted this protocol and systematically applies it to every coronary artery bypass graft performed, both in isolated and combined procedures.

Although last European Guidelines on myocardial revascularization recommended intraoperative flowmetry and ultrasound (Class IIa, evidence level B) (1), their use remains substantially limited due to the lack of familiarity with instruments and results interpretation (8).

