During surgery, every graft will be evaluated through transit time flowmetry (TTFM) and intraoperative ultrasound control (HFUS).

In details, the ultrasound control is carried out through a dedicated sterile ultrasound probe connected to a machine (MiraQ - MEDISTIM) as soon as each anastomosis is completed. The result of the evaluation is recorded together with surgery data. This evaluation is intended to confirm the correct realization of the anastomosis and provides a proof of its patency.

Once each graft is completed, the resident will be given 60 seconds to acquire two HFUS recordings (short and long axis). After that, the supervisor will perform his personal recording which will stand as benchmark. The following items will be evaluated:

- A) Long axis recording acquired within 60 seconds [YES → 1] [NO → 0]
- B) Long axis recording judged as suitable by the supervisor [YES → 1] [NO → 0]
- C) Short axis recording acquired within 60 seconds [YES → 1] [NO → 0]
- D) Short axis recording judged as suitable by the supervisor [YES → 1] [NO → 0]

E) Correct interpretation of the anastomosis as adequate or inadequate [YES → no penalty] [NO → total score becomes 0 and the resident isn't allowed to perform TTFM]

Each resident will be given a HFUS-related score from a minimum of 0 to a maximum of 4. Whenever one of the recordings will be judged as non-suitable by the supervisor and consequently useless for a correct interpretation of the anastomosis (score 0 for items A and/or C), item E won't be evaluated and the HFUS will be given a total score of 0.

Next step will be the TFM evaluation, which is carried out through a specific sterile device connected to the same machine (MiraQ - MEDISTIM) once the patient has been weaned from the cardiopulmonary bypass and before protamine administration. This recording is performed under EKG and pressure-controlled conditions. Although there is no general agreement on the optimal mean arterial pressure at which the measurement has to be recorded, we will adopt the standard used in the REQUEST study protocol (16), that is an average pressure of 80 mmHg.

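### Item N scores backward flow, a percentage with a 3 percent cut-off, by undefined 10%/20% deltas: too strict if relative, almost automatic if in percentage points

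*Combined protocol and SAP*

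**What the plan says.** The Background defines the quantity as a percentage: "Backward flow (BF - percentage): it represents the percentage of flow directed from the native coronary artery to the graft during a cardiac cycle". It reports an "identified cut-off of 3 percent of the total flow" and concludes that "a retrograde flow area >3 percent of the total graft flow area represents a risk factor for failure".

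In the TTFM items of Study Procedures, the resident's value is compared with the supervisor's: "N) Backward Flow [delta between resident and supervisor measurements". A delta below 10% earns 1, one between 10% and 20% earns 0.5, and one above 20% earns 0. ACI, mean flow, pulsatility index and diastolic filling use the same bands. The text does not say whether delta is relative or in percentage points. It names no denominator, gives no rule for a reading of 0, and assigns no score at exactly 10% or 20%.

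The item feeds two endpoints. The primary one is "Number of anastomoses needed to reach a ratio (total score/n. of anastomoses) ≥ 11"; the secondary TTFM one requires a mean of at least 7.

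**The concern.** Bands of 10% and 20% can work as relative differences for a measure such as mean flow, where the guideline value cited is above 20 ml/min. Backward flow is different: its decision value is 3, and readings at or near 0 are possible. A relative band then shrinks towards nothing, while a band of 10 percentage points is more than three times the cut-off.

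Residents continue until their cumulative mean score reaches 11, and the study may be considered complete once all eight have reached it. If delta is relative, a recurring loss caused by measurement noise would lengthen a resident's count, or keep the threshold out of reach, for reasons unrelated to skill. If delta is in percentage points, the item adds a nearly free point and says little about whether the resident's measurement agrees with the supervisor's.

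**Working it through.** **The plan's maximum and the slack.** "Each resident will be given a HFUS-related score from a minimum of 0 to a maximum of 4" (items A to D). "Each resident will be given a TTFM-related score from a minimum of 0 to a maximum of 8" (items F, G, H, I, L, M, N and O, 1 point each). The plan states a maximum of 12 for the two together, and this reproduces: 4 + 8 = 12. Slack is 12 − 11 = 1 point per anastomosis on average for the primary endpoint, and 8 − 7 = 1 for the TTFM endpoint.

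**Relative delta, without any assumption.** The full-mark tolerance is 0.1 × BF and the half-mark tolerance 0.2 × BF, where BF is the supervisor's backward flow.
- BF 0: division by zero, so no score exists.
- 1.0 v 1.3: 0.3/1.0 = 30%, score 0, although both values lie well below 3.
- 3.0 v 3.7: 0.7/3.0 = 23%, score 0.
- 1.0 v 1.1: 0.1/1.0 = 10%, a boundary with no assigned score; with the other value as denominator, 0.1/1.1 = 9.1%, score 1.

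**Relative delta, expected loss.** Assume resident and supervisor are equally precise and unbiased, each reading having error SD s around the same true BF. Their difference D then has SD s√2, and

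expected loss = 1 − ½ [P(|D| < 0.1 BF) + P(|D| < 0.2 BF)], with P(|D| < t) = 2Φ(t / (s√2)) − 1.

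Example, BF 1% and s = 0.2: s√2 = 0.283; the probabilities are 0.276 and 0.521; loss = 1 − ½ (0.797) = 0.60.

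| True BF | Full / half tolerance (percentage points) | Loss, s = 0.2 | s = 0.3 | s = 0.5 |
|---|---|---|---|---|
| 1% | 0.1 / 0.2 | 0.60 | 0.73 | 0.83 |
| 3% | 0.3 / 0.6 | 0.16 | 0.32 | 0.53 |
| 5% | 0.5 / 1.0 | 0.04 | 0.13 | 0.32 |

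Simulating readings rounded to 0.1 and cut off at 0, with the exact 10% and 20% boundaries given the higher score, yields nearly the same ranges: 0.58 to 0.82, 0.16 to 0.53 and 0.04 to 0.32. At a true BF of 0.5% with s = 0.3, the supervisor reads 0.0 in Φ((0.05 − 0.5)/0.3) = Φ(−1.5), about 7% of grafts, and the item cannot be scored.

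**Percentage-point delta.** The tolerances become 10 and 20 points. The same formula gives an expected loss of 0.00 when D has an SD of up to 2 points, 0.0004 at 3 and 0.02 at 5. Readings of 1% v 4% (3 points apart) and 2% v 11% (9 points apart) both score 1, although each pair straddles the 3 percent cut-off.

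**The case against.** A reader might infer that item N uses up most of the 1-point slack whichever way delta is taken. The documents do not support that. The two interpretations err in opposite directions: only the relative one consumes slack, and the percentage-point one gives the point away. Even under the relative one, losing most of the slack needs both low backward flow and a reading SD that the documents do not supply. At 5% with an SD of 0.3 the expected loss is 0.13, and at 3% with an SD of 0.2 it is 0.16.

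It is also tempting to say that residents are penalised most when grafts are best. The Background says that values above 3 percent are a risk factor; it gives no distribution of readings in good grafts, so this remains an inference.

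On 2% v 11%, one can answer that items I to O score agreement, while item P penalises misjudging the graft by setting the score to 0. That stands as far as classification goes: item N need not classify around 3 percent. It does not rescue the item as a measure of agreement, since a 9-point gap on this quantity still counts as full agreement.

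Finally, item N is not the only drain. Item H as printed gives 0 when no probe change is needed, which alone takes the full 1 point on such grafts. That is a separate defect; it leaves less room to absorb a loss on item N.

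**Conclusion.** The point holds in a limited form, and it is more than a missing definition, because choosing either interpretation leaves a faulty item. That conclusion rests on the documents alone: the unit, the 3 percent cut-off and the printed bands.

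The size is conditional. If delta is relative, item N can cost up to the full 1 point on a low-backward-flow graft. The average loss for a fully precise resident is about 0.6 to 0.8 at 1%, 0.2 to 0.5 at 3% and 0.04 to 0.3 at 5%, assuming normal, unbiased errors with an SD of 0.2 to 0.5 percentage points per reading. The effect on the number of anastomoses cannot be computed without that SD and the distribution of backward flow. If delta is in percentage points, no meaningful slack is lost and the item hardly discriminates. The change is worth making before scoring starts, since the item enters both the primary and the TTFM endpoint.

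**What to change.** Score item N on an absolute scale with a tolerance suited to a quantity whose cut-off is 3 percent. For example: 1 if the readings differ by no more than 1 percentage point, 0.5 if by more than 1 and up to 2, and 0 otherwise. Then 0 v 0 and 1.0 v 1.3 score 1, and 2 v 11 scores 0. Under the same noise model the expected loss is 1 − ½ [P(|D| < 1) + P(|D| < 2)]: below 0.001 at an SD of 0.2 per reading, 0.01 at 0.3 and 0.08 at 0.5.

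Keep relative deltas for mean flow and pulsatility index, naming the supervisor's value as denominator and assigning the exact 10% and 20% boundaries. State the scale for diastolic filling, which is also a percentage. Leave graft classification to item P. Making full marks for item N also depend on both readings lying on the same side of 3 percent would penalise equal operators at a true value of 3%: with half marks when only one condition holds, the expected score is 0.76, against 0.84 under the present relative rule, at an SD of 0.2.

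As a sensitivity check, report the primary and TTFM endpoints once without item N, lowering maximum and threshold by 1 point each (10 of 11, and 6 of 7).

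The cost is a short edit to the scoring list and one extra tabulation from readings already collected. The band is a convention and must be fixed before scoring starts. Above 10% backward flow, its 1-point full-mark tolerance is stricter than the relative one (0.1 × 10 = 1).

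### The primary end-point is a cumulative mean from the first graft, stopped at first crossing with no minimum count, so it mixes first-graft chance and pay-back of early errors with the point at which a resident reaches the target

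*Combined protocol and SAP*

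**What the plan says.** Under Study Procedures, each graft receives an HFUS score (0 to 4) and a TTFM score (0 to 8), which are added to give a graft score between 0 and 12. The individual stopping rule follows: "Each resident will continue until reaching a ratio between total score and number of evaluated anastomoses of 11". Under End-points, the primary end-point is "Number of anastomoses needed to reach a ratio (total score/n. of anastomoses) ≥ 11". The secondary end-points use the same form of ratio.

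Errors can produce zeros in three ways:

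- A wrong reading of the anastomosis (item E): "total score becomes 0 and the resident isn't allowed to perform TTFM".
- A recording judged unsuitable: "item E won't be evaluated and the HFUS will be given a total score of 0". This concerns the HFUS part.
- A wrong reading of graft quality (item P, in the TTFM list) sets a total score to 0. The text does not say whether that is the TTFM total or the graft total.

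Under Study Design and Duration, the trial "could be considered completed when all the eight cardiac surgery residents involved have reached primary endpoint". The documents give no minimum number of grafts, no moving window and no requirement to hold the level. The statistical analysis section lists descriptive summaries and two-group tests, but no learning-curve method.

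**The concern.** The primary objective is the complexity of the residents' learning curve. For a count of grafts to describe that curve, it should depend mainly on how performance develops. Two features of the rule work against this.

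- **First crossing with no minimum.** One high score at the start ends a resident's participation, whether or not the level would have been held.
- **Carry-over.** Every early low score remains in the mean. The target (11) lies only 1 point below the maximum (12), so early shortfalls are paid back slowly.

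Both situations are plausible here. Residents have different levels of training and attend a lesson and workshop first, so a high first score can occur. The Background itself expects diagnostic errors at the beginning, and the scoring penalises them with zeros.

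The same ratio is the primary end-point, the individual stopping rule and, through the requirement on all eight residents, the completion rule. Once a resident has stopped, later grafts are not scored, so the analysis cannot recover the missing information. With eight residents, one or two extreme counts can change the main result.

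**Working it through.** **The plan's own figure.** 8 residents × about 10 surgeries = 80 patients, which matches the sample size section. It counts surgeries while the end-point counts anastomoses, and no number of grafts per surgery is given. It therefore does not bear on the arithmetic below.

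**Inputs from the documents.** Maximum graft score 12; threshold 11; divisor is the number of evaluated anastomoses; zeros as listed above.

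**First graft.** At n = 1 the ratio equals the first score. Any of 11, 11.5 or 12 meets the end-point, so the recorded count is 1.

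**Carry-over.** Suppose j early grafts score v and are followed by m flawless grafts. The threshold is met when jv + 12m ≥ 11(j + m), that is m ≥ j(11 − v). The recorded count is n = j + j(11 − v).

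| Early scores | Flawless grafts needed | Recorded count |
|---|---|---|
| One whole-graft zero (item E) | 11 | 12 |
| Two whole-graft zeros | 22 | 24 |
| One graft at 8 (HFUS part 0, TTFM 8) | 3 | 4 |
| One graft at 4 (item P, if only TTFM is zeroed) | 7 | 8 |
| One graft at 0 (item P, if the whole graft is zeroed) | 11 | 12 |

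These are best cases. A zero followed by 11.5s needs 11/0.5 = 22 further grafts, a count of 23. A zero followed by constant 11s, exactly the target level, never recovers. With "H) Need to change probe dimensions" scored as printed (no change = 0, change = 1), a graft without a probe change can reach at most 11 and regains nothing, so the pay-back counts are lower bounds.

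**TTFM secondary end-point.** The threshold is 7 of 8. One zero followed by 8s requires 8(n − 1) ≥ 7n, so n = 8.

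**A noise-free curve (assumed).** Scores rise evenly from 6 to 12 over 10 grafts, rounded to half points, then stay at 12. The first score of at least 11 is at graft 9. The first ten scores sum to 90, against 11 × 10 = 110. The deficit of 20 takes 20 further 12s, so the rule records 30.

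**Illustrative simulation (assumed inputs).** P(12) rises linearly from a starting value to 0.95 by graft 11, and failures score 8 or 0.

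- Starting value 0.30, zeros in 20% of failures: the true mean passes 11 at graft 10. The rule records 30% at 1 and 7% at 2 to 10; 44% have not reached it by graft 20 and 14% not by graft 40.
- Starting values 0.05 to 0.30, zeros in 0 to 20% of failures: 5 to 30% are recorded as 1, and about 0.5 to 34% have not reached it by graft 40.
- Over these settings the median count is 16 to 36 under the written rule and 11 to 13 with a window of the last 8 grafts.

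**A resident who never improves (assumed: 12 or 8 with equal chance, true mean 10).**

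| Declared finished by | Written rule | Last 8 grafts, mean ≥ 11 |
|---|---|---|
| Graft 8 | 57% | 14% |
| Graft 20 | 58% | 49% |
| Graft 40 | 58% | 79% |

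Under the written rule, 50% stop at graft 1.

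**The case against.** The strongest reply is that the ratio still carries information. The stated objective is complexity, not the date of competence. For smooth curves rising to 12 over 10 grafts from 4, 6, 8 or 10, the rule records 40, 30, 20 and 10. It ranks them correctly, though late: the first score of at least 11 is at graft 9, 9, 8 and 5. This stands, so the documents do not support a claim that the count is unrelated to learning.

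Three other strong readings are tempting and also fail.

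- *Every early error costs 11 flawless grafts.* Only item E clearly zeroes the whole graft, because it also bars TTFM. An unsuitable recording zeroes only the HFUS part, and item P is ambiguous.
- *About 30% of residents will be recorded as 1.* That figure simply restates the assumed starting probability of a 12; with 0.05 it becomes 5%. The documents give no score distribution, and the model ignores half-point scores.
- *Many residents will not finish within the planned exposure.* At 10 surgeries each, 20 or 40 grafts correspond to 2 or 4 grafts per surgery, and the plan states no such figure.

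The reply also limits the remedy. For a single early zero followed by 12s, a window of 8 gives 9 against 12, a modest gain; with two zeros it gives 10 against 24. A window is itself a first-crossing rule, and by graft 40 it passes more non-learners than the written rule does.

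**Conclusion.** The concern holds. The two faults follow from the protocol's wording and arithmetic alone: a first graft of 11 or more is recorded as 1, and early shortfalls are repaid at no more than 1 point per graft. The only reading required is that the ratio runs over all evaluated grafts from the first and stops when first met. The text does not spell this out, but the divisor and the stopping sentence say it plainly.

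The size is firm for the deterministic cases: 11, 3, and 7 or 11 flawless grafts for the three kinds of error, and 30 recorded where the assumed even curve first scores 11 at graft 9. The simulated percentages depend on assumed score probabilities and should be read only as ranges.

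The conclusion is that the count mixes first-graft chance and pay-back of early errors with the time at which performance reaches the target. A reader might go further and infer that it measures nothing about learning, or that a window would make it immune to chance; neither is supported. The rule should be changed before residents are scored, because grafts not scored after an early stop cannot be recovered.

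**What to change.** In the stopping sentence of Study Procedures and in the primary end-point, replace the cumulative ratio with a moving window, using identical wording in both places (one now says a ratio of 11, the other at least 11). For example: number of anastomoses up to and including the first k consecutive evaluated anastomoses with a mean total score of at least 11; each resident continues until this is met or the study ends.

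- Fix k in advance and justify it; k = 8 is an example, not a tested optimum.
- Use the same window for the TTFM secondary end-point, with a mean of at least 7. Since HFUS contributes at most 4, a window that meets 11 in total also meets 7 for TTFM.
- Report residents who do not reach the target as 'not reached by n', with n the number of grafts scored, and align the completion sentence with this.
- State whether item P zeroes the TTFM score or the whole graft.
- Report the chance-crossing rate for the chosen k under stated assumptions, as in the non-learner table above.

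The cost is protocol wording; the scores and patients are unchanged. The downside is that every resident must score at least k anastomoses and the smallest possible value is k, so a resident who is proficient from the start cannot be recorded below k. The HFUS secondary end-point, whose target equals its maximum, is a separate matter that this change does not settle.
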